14.3.4 Additional Analysis

Additional analysis should be run including all occurred events if the drug is given continuously.

14.3.5 Safety Test Variable Analysis

14.3.5.1 Adverse event

Analysis should be conducted for all adverse events occurred during the trial. Summarize adverse event occurrence rate, occurrence rate of specific adverse event causing the follow-up loss and occurrence rate of critical adverse event. Adverse event occurrence rate includes all adverse event occurrence rate and occurrence rate of adverse event related to the test drug.

14.3.5.2 Vital sign, physical examination

For continuous data, present technical statistics (mean, standard deviation, median, min. and max. value) on the changes between base & each visits. Based on whether the data follow normal distribution, comparatively verify between the two groups using the independent t-test or

Wilcoxon's rank sum test. Also, for comparison within each group, analyze using the paired t-test or Wilcoxon's signed rank test. For categorical data, present technical statistics (frequency, percentage) and comparatively verify between groups using the chi-square test or Fisher's exact test.

925 926

922

923

924

927 928

929

930

931

932

933

934

935

Safety (including side-effects) Evaluation Standard, Method and Reporting

15.1 Safety Related Definitions

15.1.1 Adverse Event (AE)

Adverse event is undesired and unintended signs, symptoms and diseases occurred in subjects given the test drug and does not necessarily require a direct correlation to the test drug. Therefore, it includes undesired and unintended signs (i.e. over the clinically meaningful pathological results), symptoms or diseases during the trial regardless of whether the adverse even is related to the test drug or not.

936 937 938

939

15.1.2 Adverse Drug Reaction (ADR)

Adverse drug reaction is all undesired and unintended reactions caused by any dose of the test drug and cannot disregard the correlation to the test drug.

940 941 942

943

944

945

946

947

948

949

951

952

15.1.3 Serious adverse Event (SAE)

- Serious adverse event/adverse drug reaction indicates the below cases.
 - 1) Expired or high risk of death
 - 2) In need of hospitalization or extended hospitalization. Excluding below.
 - · not related to the indication of the trial and has not deteriorated after test drug use a nd on standby or prescheduled treatment for existing symptoms
 - emergency room treatment not applying to the definition of serious adverse event and not causing hospitalization
- 950 hospitalization for the purpose of societal issues or respite care without degeneration of over all conditions
 - 3) Causing permanent disability or hypofunction
- 953 4) Fetal malformation or abnormality
 - 5) For meaningful cases requiring medical or surgical intervention to prevent subjects from being endangered or prevent the listed results from occurring

955 956

980

981

982

983

984

985

986

987

988

989

990 991

957	15.2	2 Safety Evaluation Method
958	15	5.2.1 Intensity of the Adverse Event
959	Invest	igator evaluates the intensity of the adverse event or serious adverse event occurred during
960	the te	st period. This evaluation should be based on the investigator's clinical judgment.
961	Intens	ity of the adverse events and serious adverse events recorded in the case report form should
962	refer t	o the WHO guideline and adverse events not presented should follow the below standard.
963		
964	1)	Grade1 (mild symptom)
965		Adverse events causing temporary or mild inconvenience and does not require treatment.
966		Normal life (function) of subject is not much hindered and activity not limited.
967	2)	Grdae2 (moderate)
968		Adverse events from mild to moderate limits on activity. Normal life (function) is considerably
969		hindered, requiring others' help. Treatment may be needed and once recovering from
970		treatment, treatment may not be needed.
971	3)	Grade3 (severe)
972		Adverse events with severe limitations on activities, mostly requiring others' assistance. If
973		medical treatment is needed, may require hospitalization.
974		
975	15	5.2.2 Correlation of Adverse Event
976	Corre	ation of adverse event or serious adverse event to the test drug should be based on the
977	below	guideline.
978		
979	1)	Certain

1) Certain

Correlation to test drug application/usage is valid and cannot be explained by other drugs, chemicals or current diseases. When discontinuing the test drug, show clinically reasonable reactions. If re-administered, definite pharmaceutically and phenomenologically

2) Probable/likely

Correlation to test drug application/usage is proper and cannot be explained by other drugs, chemicals or current diseases. When discontinuing the test drug, show clinically reasonable reactions (no information on re-administration)

3) Possible

Although correlation to test drug application/usage is proper, it can also be explained by other drugs, chemicals or current diseases. If information on discontinuation of the test drug is insufficient or unclear

4) Unlikely

992		If case is temporary and lacking correlation to test drug application/usage. It can also be
993		explained by other drugs, chemicals or potential diseases.
994	5)	Conditional/unclassified
995		Require more information for review for proper evaluation.
996	6)	Inaccessible/unclassifiable
997		When information is insufficient and contradictory to evaluate and cannot supplement or
998		confirm
999		
1000	15.3	Reporting of Adverse Event and Serious adverse Event
1001	Investig	ator should record all information related to adverse events and serious adverse events
1002	such as	s name of adverse event, date of occurrence, end date, continuation at the time of the final
1003	evaluat	ion, intensity, correlation to the study drug, results and treatment in the case report form.
1004		
1005	15.4	Safety Reporting
1006	If seriou	us adverse event occurs during the clinical trial, it should be reported regardless of its
1007	correlat	ion to the test drug.
1008		
1009	1) Inves	stigator
1010	Investig	ator should report all serious adverse events to the IRB immediately and should hand in a
1011	follow-u	p report with the details. In the report, the investigator should use the subject's identification
1012	number	instead of the name, social security number and address to protect the subject's personal
1013	informa	tion.
1014		
1015	,	earch Coordinator
1016	Resear	ch coordinator should report to the investigator immediately when a serious adverse event
1017	occurs.	Should also follow-up with a detailed report.
1018		
1019	3) IRB	
1020		ould advise the investigator to take necessary actions if unexpected serious adverse drug
1021		ns or new information come up which could negatively impact the subject's safety and the
1022	clinical	trial.
1023		
1024	4) Serio	ous Adverse Event Reporting
1025	Investig	ator should report all serious adverse events to the IRB immediately. If it causes death or
1026	present	s risk of death, the investigator should report within 7 days of acknowledgement and also

- hand in a follow-up report within 8 days of its first reporting. For all other serious and unexpected
- adverse drug reaction, the investigator should report to the IRB within 15 days of acknowledgement.
- Should perform follow-up research if the subject does not recover from the given serious adverse
- 1030 event after the termination of clinical test.
- 1031 While all serious adverse events should be reported until the end of the trial, serious adverse events
- occurring within 30 days from test termination, should report only those the investigator considers to
- 1033 be correlated to the test.

- 1035 5) Major Adverse Cardiac and Cerebrovascular Events [MACCE] & Bleeding Reporting
- 1036 Principal investigator or research coordinator in each institution should input in the eCRF within
- 1037 15 days of acknowledgement once a Major adverse cardiac and cerebrovascular event
- 1038 [MACCE] & bleeding occur.
- 1039 Coordinator in Seoul St. Mary's Hospital should collect the MACCE & Bleeding Event regularly
- 1040 from the eCRF and for unclear variables, should report to the CEAC (Clinical Event
- Adjudication Committee) members to receive feedback. Feedback should be reported back to
- the investigator and coordinators in each institution.

10431044

16 Informed Consent

- 1045 Investigator and research coordinator should provide a copy of the informed consent form or any
- other documents shared with the subject to the subject or representative. If there are any changes
- to the consent form or shared documents during the clinical trial, the investigator or coordinator
- should provide a copy of the revised form or document to the subject or his/her representative.

1049

1050

17 Follow-up Treatment of Subjects after Clinical Trial

- 1051 Test drugs, ticagrelor and clopidogrel are standard treatment drugs for patients with acute
- myocardial infraction based on myocardial infraction treatment standards of the American Heart
- 1053 Association and the European Heart Association. In Korea, the Health Insurance Corporation
- approves taking once of the two drugs for acute myocardial infraction. This research treats one of
- the two drugs once patients are in their stable period post 1M of myocardial infraction. Although this
- 1056 research is randomized, since there is no superiority proven for one of the drugs, patients are
- expected to certainly, and randomly choose one of drug bearing the side-effects. This research does
- not apply to the victim compensation agreement.
- 1059 Investigator should guide no-response or lost to follow-up subjects to get appropriate treatment and
- 1060 for subjects who finished the test, but experienced low efficacy of treatment, switch to other
- 1061 treatment.

1062 If serious adverse event due to the test drug occurs or the disease deteriorate during or after the 1063 clinical trial, should receive consultation or treatment anytime and will provide appropriate measures 1064 in the emergency room or clinic.

1065

1066

1067

18 Subject Safety and Protective Measures

18.1 Subject Safety and Protective Measures

- Switching from Brilinta to Pregrel has no fixed guideline, but is a possible treatment based on the investigator.
- 1070 According to the guideline of the American Heart Association, acute myocardial infarction patie
- nts must take one of the three P2Y12 inhibitors (Clopidogrel 75 mg daily, Prasugrel 10 mg da
- 1072 ily, Ticagrelor 90 mg twice daily) after drug emission stent implantation for 1 year, but there is
- no guideline as to which drug to take as a priority. (11).
- According to the research switching to clopidogrel from prasugrel among acute coronary syndrome
- patients, the effect of platelet inhibition is significantly higher in Brilinta vs. Pregrel⁽¹⁰⁾.
- 1076 However, Pregrel has been used worldwide prior to the introduction of Brilinta and is currently
- 1077 being used. Pregrel has no limitations of use as it has lower antiplatelet inhibition rate vs.
- 1078 Brilinta, but has sufficient level of platelet inhibition to show effects of treatment.
- On the contrary, as the risk of bleeding can be higher for Brilinta with its strong antiplatelet i
- 1080 nhibition, this research aims to evaluate the efficacy and safety of the two drugs.
- Test drugs are already in-market and the investigator should be fully familiar with the indicated side-
- effects and precautions in the protocol. In case there are any serious adverse events during the test,
- the investigator should terminate the clinical trial for the subject, take appropriate measures and
- 1084 immediately inform the IRB.

10851086

1087

1088

1089

1090

10911092

1093

1094

10951096

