9.2. Study Design

Screening period

To conduct screening AMI patients based on the inclusion/exclusion criteria who (1) have been treated with ticagrelor + aspirin for at least 30±7 days after an index PCI, (2) received full explanation of the study details, (3) given written consent.

To randomize eligible subjects within 30±7 days after AMI undergoing PCI with newer ge neration DES, and receiving aspirin and ticagrelor to the treatment and control groups in a 1:1 ratio.

Treatment period

Enrolled patients receive clopidogrel 75mg + aspirin 100 mg (treatment group) or ticagrelor 90mg bid +aspirin 100mg treatment (control group) for 11 months (post-AMI 1 month to 12 months) and evaluation safety and efficacy by conducting physical examination, checking vital sign, and collecting adverse events at post-PCI 3M, 6M, 12M visits.

Laboratory and imaging tests, which undergo according to the medical judgment of each investigator during the study period, are collected by reviewing medical records or EMR.

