9.5. Switching protocol (ticagrelor to clopidogrel)

In the control treatment group, when switching from ticagrelor to clopidogrel, patients take a 75mg clopidogrel without loading dose at the time of the next scheduled dose after the final dose of ticagrelor (eg, ≈12 hours from last dose of ticagrelor). The steering committee decided this switching strategy of no loading dose based on the concept that our study population would be at

424 stable status at the time point of randomization (30 days after index PCI). The data safety and 425 monitoring board (DSMB) approved this switching strategy on the condition that initial 100 enrolled 426 patients in the treatment group should be monitored daily during first 7days for the occurrence of 427 adverse clinical events by telephone interviews. Thereafter, DSMB reviewed the clinical data of the 428 initial 100 patients in the treatment group and recommended continuation of the study according to 429 the original protocol. After randomization, patients continue the same medication for 11 months 430 according to their group allocation (treatment period, Figure 1). Patients are evaluated at 3 (2) 431 months after randomization), 6 (5 months after randomization), and 12 (11months after 432 randomization) months after index PCI and monitored for the occurrence of the clinical events.

433434

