724	8) Exploratory test (Optional): Lab test, Cardiac Echo, ECG
725	
726	
727	11. Precautions and Expected Side Effects
728	11.1. Clopidogrel
729	1) Warning
730	Patients with genetic CYP2C19 hypofunction: vs. patients with normal CYP2C19 function, systemic
731	exposure of Clopidogrel's active metabolism is low. This lowers the antiplatelet reactions and
732	generally, increases the occurrence of cardiovascular events post myocardial infarction. Once
733	identified as CYP2C19 hypofunction patient, should consider alternative treatment.
734	
735	2) Adverse Event
736	Bleeding, hematological disorders (neutropenia/agranulocytosis etc.), gastrointestinal symptoms,
737	rash and other skin diseases etc.
738	
739	11.2. Ticagrelor
740	1) Warning
741	This drug can cause significant or at times, fatal bleeding as in other antithrombotic. Patients with
742	pathologic active bleeding or intracranial hemorrhage should not be given this drug. Patients should
743	stop taking this drug at least 5~7 days prior to any surgery.
744	Should suspect bleeding if patients show hypotension after taking this drug post coronary
745	angiography, percutaneous coronary intervention (PCI), coronary artery bypass graft (CABG) or
746	other surgeries. If possible, treat bleeding without discontinuing medication. If Ticagrelor treatment
747	is discontinued, risk of cardiovascular event increases.

749 2) Adverse Event

750 Bleeding, dyspnea and headache etc.

12. Withdrawal of consent or Loss of follow-up

All enrolled subjects have the right to withdraw their consent or discontinue participation in the study at any time without penalty or loss of benefits. A withdrawn subject will be treated according to the standards of medical care and will not be replaced. Subjects have the right to withdraw from the study at any time without explaining why and without any consequences. When subject discontinues from the trial, investigators record date of discontinuation, reasons for discontinuation, post-treatment and clinical course together with all the data collected until then in the case report form. If a s subject is withdrawn from the study due to problems related to the study drugs, continued follow-up will be needed for subject safety. Otherwise, no additional data will be collected after the subject withdraws. Subjects will be included in the analyses up to the time when the consent was withdrawn unless requesting no use of their medical records for the study analysis.

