14.1. General Principal of Statistical Analysis

Information collected from subjects of the present clinical trial are analyzed in two forms: ITT (Intention-To-Treatment) and PP (Per-Protocol)

792793

794

795

796

1) ITT analysis group

The ITT population is defined as all randomized patients at 1 month after AMI, regardless of their adherence with the entry criteria, regardless of treatment they actually received, and regardless of subsequent withdrawal from treatment or deviation from the protocol¹⁹. Only some specific reasons that might cause an exclusion of a patient from the ITT population:

797 798

799

- No treatment was applied at all
- No data are available after randomization

800 801 802

803

804

•

2) PP analysis group

The PP population is the subset of ITT population consisting of all patients who receive and retain the treatment during 12 months after PCI¹⁹. Some specific reasons that might cause an exclusion of a patient from the PP population:

805806807

808

809

810

811

812

813 814

815 816

- Violation of entry criteria including inclusion and exclusion criteria
- Withdrawal of consent
 - Concomitant treatment of oral anticoagulant agent (vitamin-K antagonists or novel oral anticoagulants such as dabigatran, rivaroxaban, apixaban, or edoxaban) during the study period
 - Poor compliance
 - Conversion from ticagrelor + aspirin to clopidogrel + aspirin during RCT procedure and vice versa
 - Discontinuation of test or control drugs for 7 days or longer
 - * In the cases of withdrawal of consent, concomitant treatment of oral anticoagulation agent and poor compliance, their data will be used for statistical analyses until such events occur.

818		
819		
820	3) N	∕lissing data handling
821		Missing variables will not be imputed for planned analyses, except where otherwise
822		specified.
823		• The primary endpoint will be based on Kaplan-Meier estimates, which automatically
824		account for censored data.
825		• For sensitivity, purposes, missing data was imputed the most recent data (Last
826		Observation Carried Forward method).
827	4405	
828		Evaluation Standard
829		Efficacy Test Variable
830	•	Primary Endpoint
831 832	(Composite endpoint of MACCE (CV death, MI, or stroke) + BARC bleeding (type 2, 3 or 5) between 1 and 12 months after AMI
833	2)	Main Secondary Endpoints
834	1	BARC bleeding (type 2, 3, or 5) between 1 and 12 months after AMI
835	2	
836		between 1 and 12 months after AMI

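### Section 18.1 ends the trial for a subject on any serious adverse event, which conflicts with event follow-up to 12 months; a minor trial-conduct correction

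*Protocol*

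**What the plan says.** Section 18.1 sets the trigger as "In case there are any serious adverse events during the test" and the action as "the investigator should terminate the clinical trial for the subject, take appropriate measures and" notify the IRB. The trigger is not limited to drug-related or unresolved events, and the action is not limited to study drug.

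Section 15.1.3 counts as serious "In need of hospitalization or extended hospitalization". Its exclusions are narrow: planned care for existing conditions, emergency-room visits without admission, and social or respite stays.

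The follow-up sections carry no SAE exception. Section 9.2 has 11 months of treatment, with safety and efficacy evaluated by "collecting adverse events at post-PCI 3M, 6M, 12M visits" among other checks. Section 9.5 has patients evaluated at 3, 6 and 12 "months after index PCI and monitored for the occurrence of the clinical events". The ITT definition in section 14.1 keeps all randomized patients regardless of "subsequent withdrawal from treatment or deviation from the protocol".

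Section 11.2 says of ticagrelor: "If possible, treat bleeding without discontinuing medication". Section 12 says that when a subject is withdrawn because of a study-drug problem, "continued follow-up will be needed for subject safety"; in other cases it stops data collection once the subject withdraws.

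**The concern.** A site holds two instructions for the same patient and no rule on which prevails. After an admission that is an SAE, 18.1 says the trial is over for that subject, while 9.2 and 9.5 say to keep evaluating and recording events to month 12.

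An SAE that is itself the first primary event is already counted, so nothing is lost there. Two kinds of data are exposed:

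- Primary events after a non-endpoint SAE. An example is an admission for ischemia-driven revascularization, which is a secondary endpoint outside the primary composite. The Kaplan-Meier analysis would censor that patient at the SAE, and such a patient plausibly has a higher later risk.
- Deaths or further component events after a first non-fatal MI, stroke or bleed. These feed the secondary endpoints, including all-cause and cardiovascular death.

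**Working it through.** **Comparing the sections**

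| Section | Instruction | Fits 18.1 read literally? |
|---|---|---|
| 9.2, 9.5 | Evaluate and monitor events to 12 months after PCI | No |
| 11.2 | Treat bleeding without stopping ticagrelor where possible | Poorly: a hospitalised bleed is an SAE |
| 14.1 (ITT) | Keep all randomized patients in the analysis set | Yes: the subject stays in the set, censored at the SAE |
| 12 | Follow-up continues after withdrawal for a drug problem | Partly: does not cover SAEs unrelated to the drug |
| 13 | Follow events until resolved or stable | Partly: covers the reported event, not new ones |
| 15.4 | Report all SAEs until the end of the trial | Poorly |

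**Size of the effect on the primary test**

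The protocol gives no figure to reproduce. The inputs are its control rate of 9.35%, its clopidogrel rate of 9.59%, its 3-point margin and 1,295 patients per arm. Two inputs are assumed: the share *q* of each arm with a first non-endpoint SAE who are then not followed (5% or 10%, equal in both arms), and the ratio *k* of the event hazard after that SAE to the hazard before it (1 to 3).

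Take the 11 months as one time unit, with event hazard *l* before the SAE, SAE hazard *s* = -ln(1 - *q*), and event hazard *kl* afterwards.

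- True risk: R = 1 - exp(-(l+s)) - s∫exp(-(l+s)t)·exp(-kl(1-t))dt, with t from 0 to 1. Solve for *l* so that R is 12.35% on clopidogrel (at the margin) and 9.35% on ticagrelor.
- Kaplan-Meier estimate when censoring at the SAE: 1 - exp(-l).
- Greenwood variance per arm: exp(-2l)·[l/(l+s)]·[exp(l+s) - 1]/1295.
- Probability of declaring non-inferiority: Φ((0.03 - difference)/SE - 1.96).

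Worked case, *q* = 5%, *k* = 2: s = -ln(0.95) = 0.0513. Solving gives l = 0.1287 (clopidogrel) and 0.0958 (ticagrelor). The estimates are 1 - exp(-0.1287) = 12.08% and 1 - exp(-0.0958) = 9.14%, a difference of 2.94 points. With SE 1.225 points, Φ((3.00 - 2.94)/1.225 - 1.96) = Φ(-1.911) = 2.8%.

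| Share | Hazard ratio | Clopidogrel vs ticagrelor, % | Difference, points | False non-inferiority |
|---|---|---|---|---|
| any | 1 | 12.35 vs 9.35 | 3.00 | 2.5% |
| 5% | 1.5 | 12.21 vs 9.24 | 2.97 | 2.7% |
| 5% | 2 | 12.08 vs 9.14 | 2.94 | 2.8% |
| 5% | 3 | 11.83 vs 8.95 | 2.89 | 3.1% |
| 10% | 1.5 | 12.07 vs 9.13 | 2.94 | 2.8% |
| 10% | 2 | 11.81 vs 8.93 | 2.88 | 3.1% |
| 10% | 3 | 11.35 vs 8.56 | 2.78 | 3.8% |

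At *k* = 2, about 61-62 patients per arm (5%) or 122-124 (10%) are terminated before an event. The uncollected primary events in both arms together are 7.4 + 5.7 = 13.1, or 14.6 + 11.2 = 25.8. At the planning rates (9.59% vs 9.35%) the true 0.24 points reads 0.24 or 0.23.

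**Secondary endpoints.** The planned MACCE rates give 1,295 × 5.28% = 68 ticagrelor and 1,295 × 6.60% = 85 clopidogrel patients with a MACCE event. Those whose first event is non-fatal could lose a later death or component event. These counts bound the patients exposed by a first MACCE event; they are not counts of lost events, and patients with a non-fatal bleed come on top.

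**The case against.** The strongest reply is that 18.1 is a loosely worded sentence in a subject-protection paragraph and not the follow-up rule. Much of the protocol supports this:

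- Section 12 asks for the clinical course to be recorded when a subject discontinues. It also asks for contact attempts throughout final follow-up, and counts nobody as lost until the final window closes.
- Section 13 follows events to resolution or stabilization, and section 15.4 follows up unresolved SAEs after the trial ends.
- The per-protocol exclusions in 14.1 do not mention termination for an SAE.

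This stands as evidence of intent. It makes literal data loss less likely, but no passage confines 18.1 to study drug or says that endpoint collection runs to month 12 after an SAE.

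Three stronger readings go beyond the text. A reader might infer that 18.1 contradicts the ITT definition. It does not: 14.1 fixes who is analysed, and a terminated subject remains in the set. The censoring may be informative, which undermines the purpose of ITT, but that is a different point. A reader might apply section 12's halt on data collection to subjects terminated under 18.1. That sentence concerns subjects who withdraw, so the link is an inference. A reader might also cite section 14.3.4 as proof that all later events are analysed. It applies only while the drug is given continuously, so it settles nothing here.

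**Conclusion.** The conflict between 18.1 and the 12-month follow-up in 9.2 and 9.5 is real, and 18.1 is wrong as written. It is a trial-conduct instruction to correct, not an error in the choice of analysis, and it is minor.

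The documents do not show that follow-up will stop, or that the primary result would be materially biased. With equal shares of 5-10% and a doubled later hazard, the difference at the margin shrinks by 0.06 to 0.12 points and false non-inferiority rises from 2.5% to 2.8-3.1%. With equal shares and a raised hazard the shift favours non-inferiority; with an unchanged hazard there is no bias. Higher or unequal shares could do more. With unequal shares the direction depends on the arm, and section 12's provision for drug problems would limit a drug-caused imbalance.

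The shares and hazard ratios are assumptions. The 2.5% baseline takes the two-sided 95% interval as the decision rule, although 14.3.1 also states a one-sided 0.05 test. The loss to the secondary endpoints cannot be sized from the protocol.

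**What to change.** Reword the sentence in 18.1 along these lines: *On a serious adverse event, stop study drug if clinically required; continue endpoint collection to 12 months, by telephone if needed, unless the subject withdraws consent to follow-up.* Keep the IRB notification as it is.

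As a minor clarification, section 12 could say that its halt on data collection applies only when the subject withdraws consent to follow-up. No added analysis is needed.

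The cost is one sentence, one optional line and a little extra follow-up contact. The time table already allows a call when a visit is not feasible. Subject protection is unchanged, because the investigator can still stop the drug.
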